6.3.4 Analysis of Safety

The incidences of AEs and SAEs reported from the start of deferiprone therapy for all patients will be tabulated. For patients continuing on deferiprone, this time period will be from the start of LA38-0411 to the completion of LA38-EXT; for those switching to deferiprone, it will be from the start of LA38-EXT to the completion of LA38-EXT. AEs will be summarized by worst severity and by relationship to the study medication. Time to onset and duration of all SAEs, of AEs of special interest such as neutropenia, agranulocytosis, increased ALT, and arthralgia: 1) the mean time to the first onset and the mean time to the last recurrence will be calculated, and 2) the mean duration for the first episode and the mean duration for any recurrent episodes, excluding the first episode, will be calculated for all SAEs and AEs of special interest.

The percentage of discontinuations due to AEs will be calculated, and the AEs leading to discontinuation will be summarized in a frequency table.

Laboratory data (hematology and chemistry) will be summarized using descriptive statistics for continuous variables and frequency tables for discrete variables. The incidences of out-of-range data will be tabulated, and the changes from baseline to the end of study will be presented in shift tables.

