Changes in LIC, in cardiac MRI T2*, and in serum ferritin from baseline to Year 1(both groups; Group 1 data are from LA38-041), from baseline to Year 2 (both groups), and from baseline to Year 3 (Group 1 only) will be summarized with descriptive statistics, and will be tested against no change using a one-sample t-test. The changes in these 3 efficacy measures from the start of deferiprone therapy to the last visit of LA38-EXT in all patients, irrespective of whether deferiprone therapy was initiated in LA38-0411 or in LA38-EXT, will also be tested using a one-sample t-test. In addition, the percentages of responders will be tabulated for Year 1 (both groups; Group 1 data are from LA38-0411), for Year 2 (both groups), and for Year 3 (Group 1 only) of

	deferiprone therapy.
	Additional statistical analysis may be performed if deemed necessary. Details will be provided in the statistical analysis plan.
Version and date of the protocol:	Version 3.1, 01 MAY 2017

TABLE OF CONTENTS

S	GNATUF	RE PAGES	2
S	YNOPSIS		4
L	IST OF IN	N-TEXT TABLES	11
L	IST OF A	BBREVIATIONS AND DEFINITIONS OF TERMS	12
1	INT	RODUCTION	13
	1.1 Ba	ackground	13
	1.1.1	Sickle Cell Disease	13
	1.1.2	Ferriprox [®]	14
	1.2 Ra	ationale	15
	1.3 Po	otential Risks and Benefits	15
2	STU	DY OBJECTIVES	18
	2.1 Pr	imary Objective	18
	2.2 Se	econdary Objective	18
3	STU	DY DESIGN	18
	3.1 De	escription of Study Design	18
	3.2 Ra	ationale for Study Design	18
	3.3 Ra	ationale for Selection of Doses	18
4	STU	DY POPULATION	20
	4.1 N	umber of Patients	20
	4.2 In	clusion Criteria	20
	4.3 Ex	xclusion Criteria	20
	4.4 E1	nrolment Violations	21
	4.5 Pa	ntient Withdrawal	21
	4.5.1	Follow-up of Patient Withdrawal Due to Pregnancy	22
	4.5.2	Replacement of Patients Who Withdraw	23
	4.5.3	Treatment Interruptions	23
	4.6 Pr	ior and Concomitant Therapies	24
	4.7 Re	escue Medication	24
5	STU	DY PROCEDURES	24
	5.1 V	isit Procedures	27

	5.2	Method	d of Assignment to Treatment	39
	5.3	Blindir	ng Procedures	39
	5.4	Allocat	tion of Patient Numbers	39
	5.5	Treatm	ent Compliance	39
6	S	TUDY T	FREATMENTS	39
	6.1	Investi	gational Product	40
	6.1	1.1 Do	osage Form and Mode of Administration	40
	6.1	1.2 Pr	ecautions for Use	40
	6.2	Referei	nce Product	40
	6.3	Packag	ging and Labeling	40
	6.4	Shippii	ng and Storage	40
	6.5	Produc	t Accountability	40
	6.6	Replac	ement Doses	41
	6.7	Dispos	ition of Unused Product	42
	6.8	Other S	Study Supplies	42
7	N	MEASUI	REMENTS AND EVALUATIONS	42
	7.1	Efficac	y Measurements	42

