9 STATISTICAL ANALYSIS

9.1 Endpoints

9.1.1 Primary Endpoints

- Adverse events (AEs): Frequency, severity, time to onset, duration, and relatedness to study product
- Serious adverse events (SAEs): Frequency and relatedness to study product
- Number of discontinuations due to AEs

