2 STUDY OBJECTIVES

2.1 Primary Objective

To evaluate the long-term safety and tolerability of deferiprone in iron-overloaded patients with sickle cell disease or other anemias.

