6 STATISTICAL ANALYSIS

6.1 Endpoints

6.1.1 Primary Endpoints

- Adverse events (AEs): Frequency, severity, time to onset (the start date of AE minus the start date of exposure to treatment), duration (the stop date of AE minus the start date of AE), and relatedness to study product
- Serious adverse events (SAEs): Frequency and relatedness to study product
- Number of discontinuations due to AEs

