17 TABLE SHELLS

The following table shells provide a framework for the display of data from this study. These tables may not be produced exactly as shown in the shells, but are intended to reflect the general layout of the data that will be included in the clinical study report.

Note that 'c' in the table shells indicates an alphanumeric character and 'x' indicates a number from 0 to 9.

If the same data points are collected at more than one visit, the results will be summarized in Table x.x for baseline, x.x-1 for visit 1, x.x-2 for visit 2 and so on.

Table 14.1.1 Patient disposition

	Treatment	
	DFP+ DFP	DFO+DFP
Enrolled	Xxx	xxx
Exposed*	xxx (xx%)	xxx (xx%)
Completed*	xxx (xx%)	xxx (xx%)
Withdrawn*	xxx (xx%)	xxx (xx%)

Data source: 16.2.18 Listing of disposition

Note: *Percentages are based on the number of enrolled patients in each treatment group.

Table 14.1.2 Number of patients in the ITT, PP, and safety populations

		Treatment	
		DFP+DFP	DFO+DFP
ITT population	LIC	xxx	xxx
	Cardiac MRI T2*	xxx	xxx
	Serum Ferritin	xxx	xxx
PP population	LIC	xxx	xxx
	Cardiac MRI T2*	xxx	xxx
	Serum Ferritin	xxx	xxx
Safety population		xxx	xxx

Data source: 16.2.10 Listing of LIC, 16.2.11 Listing of cardiac MRI T2*, and 16.2.16 Listing of serum ferritin, and 16.2.24 Listing of exposure

Table 14.1.3 Number of patients by study site

Study Site	Treatment	
	DFP+DFP	DFO+DFP
001	xxx	xxx
002	xxx	xxx
...
Total	xxx	xxx

Data source: 16.2.2 Listing of demographics

Table 14.1.4 Reasons for not completing the study

	Reason	Treatment	
		DFP+DFP	DFO+DFP
N (%)		xx (100)	xx (100)
Adverse event	Detail		
	Ccccc	xx (xx)	xx (xx)
	Ccccc	xx (xx)	xx (xx)
Voluntary withdrawal	Ccccc	xx (xx)	xx (xx)
	Ccccc	xx (xx)	xx (xx)
Lost to follow-up	Ccccc	xx (xx)	xx (xx)
	Ccccc	xx (xx)	xx (xx)
Investigator decision	Ccccc	xx (xx)	xx (xx)
	Ccccc	xx (xx)	xx (xx)
Protocol violation	Ccccc	xx (xx)	xx (xx)
	Ccccc	xx (xx)	xx (xx)
Other	Ccccc	xx (xx)	xx (xx)
	Ccccc	xx (xx)	xx (xx)
Total		xx (xx)	xx (xx)

Data source: 16.2.18 Listing of disposition

Table 14.1.5 Demographics data

	Treatment		p-value [§]
	DFP+DFP	DFO+DFP	
N	Xxx	xxx	
Age (years): Mean \pm SD (Min, Median, Max)	xx.x \pm xx.x (xx.x, xx.x, xx.x)	xx.x \pm xx.x (xx.x, xx.x, xx.x)	0.xxxx
Sex: n (%) Female Male	xx (xx) xx (xx)	xx (xx) xx (xx)	0.xxxx
Ethnic Origin: n (%) Hispanic/Latino Other	xx (xx) xx (xx)	xx (xx) xx (xx)	0.xxxx

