Table 14.2.3.3 Change in serum ferritin for DFO+DFP group – Data from the extension study

		DFO+DFP	
	Visit	N Mean ± SD (Min, Max)	P-value (One sample T-test)
Change in serum ferritin (µg/L)	From Month 12 to Month 15	XXX XX.X ± XX.X (xx.x, xx.x)	0xxxx
	From Month 12 to Month 18	XXX XX.X ± XX.X (xx.x, xx.x)	0xxxx
	From Month 12 to Month 21	XXX XX.X ± XX.X (xx.x, xx.x)	0xxxx
	From Month 12 to Month 24	XXX XX.X ± XX.X (xx.x, xx.x)	0xxxx
	From Month 12 to Month 27	XXX XX.X ± XX.X (xx.x, xx.x)	0xxxx
	From Month 12 to Month 30	XXX XX.X ± XX.X (xx.x, xx.x)	0xxxx

		DFO+DFP	
	Visit	N Mean \pm SD (Min, Max)	P-value (One sample T-test)
	From Month 12 to Month 33	xxx xx.x \pm xx.x (xx.x, xx.x)	0.xxxx
	From Month 12 to Month 36	xxx xx.x \pm xx.x (xx.x, xx.x)	0.xxxx

Data source: 16.2.16 Listing of serum ferritin

Table 14.2.3.4 Responder analysis in serum ferritin as defined $\geq 20\%$ decline in serum ferritin from baseline.

	Treatment				P-value (Fisher's exact test)	
	DFP+DFP		DFO+DFP			
	N	n (%)	N	n (%)		
Year 1	xxx	xx (xx%)	xxx	xx (xx%)	0.xxxx	
Year 2	xxx	xx (xx%)	xxx	xx (xx%)	0.xxxx	
Year 3	xxx	xx (xx%)	xxx	xx (xx%)	0.xxxx	

Data source: 16.2.16 Listing of serum ferritin

Table 14.2.3.5 Responder analysis in serum ferritin defined as $\geq 20\%$ decline in serum ferritin from baseline for DFP+DFO group – Data from the extension study.

	Treatment	
	DFO+DFP	
	N	n (%)
Year 1	xxx	xx (xx%)
Year 2	xxx	xx (xx%)

Data source: 16.2.16 Listing of serum ferritin

Table 14.3.1.1 Overall summary of adverse events

	Treatment		P-value (Fisher's exact test)
	DFP+DFP	DFO+DFP**	
N	xxx	xxx	
Number of patients experiencing at least one AE	xx (xx%)	xx (xx%)	0.xxxx
Number of patients experiencing at least one severe AE	xx (xx%)	xx (xx%)	0.xxxx
Number of patients experiencing at least one serious AE	xx (xx%)	xx (xx%)	0.xxxx
Number of patients experiencing at least one related* AE	xx (xx%)	xx (xx%)	0.xxxx
Number of patient deaths	xx (xx%)	xx (xx%)	0.xxxx
Number of patient withdrawals due to AEs	xx (xx%)	xx (xx%)	0.xxxx

*Includes possibly, probably, and definitely related. Worst case scenario of causality between the investigator and company's assessment.

**AEs occurred while on DFP treatment.

Data source: 16.2.23 Listing of adverse events

Table 14.3.1.2 Adverse events

		Treatment		
		DFP+DFP (N=xxx)	DFO+DFP (N=xxx)	
Exposure (patient-years): x.xx		Exposure (patient-years): x.xx		
Total Events: xxx		Total Events: xxx		

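### Safety table shells test three years of adverse events in one group against two years in the other, with no adjustment for exposure or censoring

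*SAP*

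**What the plan says.** SAP 6.3.4 counts AEs and SAEs from the start of deferiprone. For Group 1 (DFP+DFP), "For patients continuing on deferiprone, this time period will be from the start of LA38-0411 to the completion of LA38-EXT". For Group 2 (DFO+DFP) the window is LA38-EXT alone, and a footnote to shell 14.3.1.1 confirms the restriction: "AEs occurred while on DFP treatment". Protocol 1.2 gives the same arithmetic: a total of two or three years on deferiprone, depending on the earlier assignment.

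For SAEs and AEs of special interest, 6.3.4 adds that "the mean time to the first onset and the mean time to the last recurrence will be calculated". SAP 6.1.1 defines "time to onset (the start date of AE minus the start date of exposure to treatment"), so a patient without the event has no value. The body text names no between-group test for safety.

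The tests appear in the shells (SAP section 17):

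- **14.3.1.1 and 14.3.1.2**, with 14.3.1.3–14.3.1.7 by reference, compare the number (%) of patients with an event between groups by Fisher's exact test. Patient-years appear as a column header in 14.3.1.2 and the tables that follow its layout, but do not enter the test.
- **14.3.1.9 and 14.3.1.11**, with 14.3.1.10 and 14.3.1.12 by reference, compare mean time to first onset and to last recurrence by t-test.

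Neither 6.3.4 nor these shells provides an exposure-adjusted rate, a common window or censoring.

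**The concern.** Two groups with exactly the same risk on deferiprone will differ in these tables because one is watched for a year longer. More patients have had at least one event by Month 36 than by Month 24. Among those who did, onset can be as late as Month 36 in one group but not beyond Month 24 in the other. A small p-value may then mean only that three years is longer than two.

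A second effect depends on the meaning of *enrolled* in SAP 6.2.3. Protocol 4.5.2 admits only LA38-0411 completers. If the safety population means patients enrolled in LA38-EXT, Group 1 patients who left during their first deferiprone year because of an AE are absent, while Group 2 is followed from its first dose. This selection lowers Group 1's frequency and pushes its onsets later. It can offset or reverse the window effect on frequency, but it adds to the effect on onset.

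The affected quantities are primary endpoints: Protocol 9.1.1 lists, for AEs, "Frequency, severity, time to onset, duration, and relatedness to study product". What is at stake is a safety report showing a group difference, or a gap in mean onset, that does not reflect risk.

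**Working it through.** The plan gives no alpha, AE rate or sample size for these tests, so there is no planned figure to reproduce. The question is how often the tests reject when risk on deferiprone is identical.

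**Inputs from the documents**
- Windows: 3 and 2 years (SAP 6.3.4).
- Parent study: 300 planned, 2:1 (Protocol 1.2), so at most 200 and 100.
- Frequencies among 712 treated patients (Protocol 1.3): agranulocytosis 2.1%, neutropenia 6.9%, ALT increased 7.6%, arthralgia 10.5%. SAP 6.3.4 names these four as events of special interest.

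**Assumptions**
- 160 vs 80 patients (80% of 300 entering); 120 vs 60 (60%) in brackets.
- The Protocol 1.3 frequencies are two-year risks. The protocol gives no exposure time for them.
- Two-sided 5% level, no dropout.

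**Risk model.** F(t) = 1 − exp(−H·(t/2)^k), with H = −ln(1 − two-year risk). k = 1 is constant hazard; k = 0.5 is front-loaded.

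**Rejection with no true difference.** Fisher is by exact enumeration. The t-test is by 20,000 simulated trials, among trials with at least two cases per group.

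| Two-year risk, both groups | Three-year risk, k = 1 | Fisher, k = 1 | Onset t-test, k = 1 | Fisher, k = 0.5 | Onset t-test, k = 0.5 |
|---|---|---|---|---|---|
| 2.1% | 3.1% | 2.0% (1%) | 8% (9%)* | 1.8% | 5.3% |
| 6.9% | 10.2% | 9.4% (7%) | 16% (12%) | 4.5% | 6.1% |
| 7.6% | 11.2% | 10.5% (7%) | 17% (13%) | 4.7% | 6.6% |
| 10.5% | 15.3% | 14.9% (10%) | 25% (18%) | 6.1% | 9.0% |

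*At 2.1% the t-test can be computed in only 48% (32%) of trials. Over all trials rejection is about 0.48 × 8.3% = 4% (0.32 × 9% = 3%).

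With both groups cut at 24 months, Fisher rejects in 2–4% and the t-test in 5–6%. The excess comes from the window.

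**Mean onset among cases.** For k = 1 the mean is 1/h − T·e^(−hT)/(1 − e^(−hT)). At 10.5%, h = −ln(0.895)/2 = 0.0555 per year.
- T = 3: 18.03 − 3 × 0.8467/0.1533 = 1.46 years = 17.5 months.
- T = 2: 18.03 − 2 × 0.895/0.105 = 0.98 years = 11.8 months.

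Across the four rates the gap is 5.7–5.9 months for k = 1 and 3.8–4.0 months for k = 0.5 (11.6 vs 7.8 at 10.5%).

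**Last recurrence.** For a Poisson rate and at least two events, the mean is T·E[N/(N+1)]. Rates of 0.1, 0.3 and 1.0 per year give 24.3 vs 16.1, 24.9 vs 16.4 and 27.4 vs 17.5 months.

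**Commoner events.** Hazards of 0.1, 0.2 and 0.3 per year are assumed, not documented. Fisher rejects in 24, 41 and 51% (18, 31, 40%), and the t-test in 43, 65 and 71% (31, 50, 56%).

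**Completer selection at the 10.5% rate.** If a share f of year-1 cases left before LA38-EXT, Group 1's risk is (F(3) − f·F(1))/(1 − f·F(1)). For k = 1, f = 0.25: (0.1533 − 0.25 × 0.0540)/(1 − 0.25 × 0.0540) = 14.2%. Group 2 stays at 10.5%. Results are for 160 vs 80.

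| k | f | Group 1 frequency | Fisher | Onset t-test | Onset gap (months) |
|---|---|---|---|---|---|
| 1 | 0.25 | 14.2% | 10% | 37% | 6.8 |
| 1 | 0.50 | 13.0% | 7% | 55% | 8.2 |
| 0.5 | 0.25 | 11.0% | 4% | 16% | 5.2 |
| 0.5 | 0.50 | 9.3% | 5% | 32% | 7.1 |

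**The case against.** The strongest reply is that nothing is decided on these p-values. The objective is not comparative: "To evaluate the long-term safety and tolerability of deferiprone in iron-overloaded patients with sickle cell disease or other anemias". The safety text of both documents plans tabulations and means only, and SAP section 17 says of its shells, "These tables may not be produced exactly as shown in the shells, but are intended to reflect the general layout of the data". This stands as a limit on consequence. But the shells are the only place where these tests are specified, and their specification is wrong.

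Patient-years are also printed above most of the AE tables, so a reader can see the imbalance. True, but the p-value beside the counts ignores it.

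The size is open to challenge, and several points stand:
- The only hazard-shape evidence in the documents is for agranulocytosis, said in Protocol 1.3 to peak at 5 months and then decline. In the front-loaded case rejection is near nominal. The k = 0.5 curve puts its peak at time zero, so it only approximates that pattern.
- The Protocol 1.3 frequencies are reactions judged at least possibly related, so they fit the adverse-drug-reaction tables better than all-cause AEs or individual SAE terms. Rare terms are little affected.
- The selection effect rests on one reading of *enrolled* and on attrition shares that the documents do not give.

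None of this removes the gap in mean onset, which remains at 3.8 months or more in every onset scenario tabulated for the protocol's rates.

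Finally, deleting the p-values or cutting both groups at 24 months would be a smaller repair. A 24-month cut does restore nominal error, but it drops Group 1's third year from the comparison and leaves completer selection in place.

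**Conclusion.** The concern holds. As specified, the shells put p-values on primary safety endpoints that mix risk with follow-up length and, on one reading of the safety population, with completer selection.

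At the protocol's own event frequencies, with 160 vs 80 patients and constant hazard, false rejection reaches 15% for Fisher and 25% for the onset t-test. It is larger for commoner events and near nominal for rare or early-onset ones. The distortion of mean onset is about 4 to 6 months from window length alone. These sizes rest on assumed sample sizes, no dropout, and reading the protocol's frequencies as two-year risks. The mechanism does not.

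The direction of the frequency bias is not assured if early leavers are excluded. The plan should be corrected, although no confirmatory conclusion depends on it.

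**What to change.** In SAP 6.3.4 and the shells:

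1. Remove the between-group p-values from Tables 14.3.1.1–14.3.1.7 and 14.3.1.9–14.3.1.12.
2. Add first-event rates per 100 patient-years with confidence intervals, by group and by year on deferiprone (0–12, 12–24, 24–36 months). One pooled rate is not enough: at the 10.5% risk with k = 0.5 it gives 4.6 vs 5.7 at identical risk. The by-year rates (7.95, 3.25, then 2.49 in Group 1 only) agree where both groups are observed, absent selection.
3. Keep the protocol-specified mean onset and last-recurrence times as within-group description. Add Kaplan–Meier or cumulative-incidence onset estimates that censor event-free patients at end of exposure, and a recurrence rate per patient-year.
4. State in 6.2.3 whether *enrolled* means enrolled in LA38-EXT. If so, footnote that Group 1's first year is conditional on completing LA38-0411, and label side-by-side displays as descriptive. Censoring does not cure this: with half of year-1 cases lost, the Month 24 Kaplan–Meier risk in Group 1 would read 8.0% (k = 1) or 7.0% (k = 0.5) against a true 10.5%.

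The cost is SAP wording and some rate and survival programming. Exposure is already listed (16.2.24), and 6.3.4 already draws on LA38-0411 events for Group 1. The protocol synopsis leaves room: "Additional statistical analysis may be performed if deemed necessary", with details in the SAP. Conduct, data collection and the safety population do not change. The price is fewer p-values and some extra tables, with sparse cells for rare terms.

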1.2 Rationale

ApoPharma Inc. is currently conducting a 12-month trial, study LA38-0411, to assess the safety and efficacy of deferiprone in patients with SCD or other anemias that necessitate regular blood transfusions (excluding thalassemia syndromes, MDS, myelofibrosis, Diamond Blackfan anemia, and primary bone marrow failure). In that study, a planned 300 participants will be randomized in a 2:1 ratio to receive either deferiprone or deferoxamine. Assessments include weekly, biweekly, or monthly monitoring of absolute neutrophil count (ANC); monthly assessments of adverse events, hematology, biochemistry, and vital signs; quarterly assessments of serum ferritin; and semi-annual serology, ECG, liver iron concentration (LIC) as measured by MRI, cardiac MRI T2*, and quality-of-life questionnaires.

Patients who complete study LA38-0411will be invited to enroll in the current study, LA38-EXT, in which all participants will receive deferiprone. Participants will thus receive deferiprone for a total of either 2 years or 3 years, depending on which treatment was assigned in the earlier study. The long-term data obtained will provide additional information on the safety and efficacy of deferiprone in patients with sickle cell disease or other anemias.

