Because of the awareness of this risk, weekly monitoring for neutrophil count was proposed in the first marketing authorization application for deferiprone and has been in effect since. However, a recent review of both clinical and post-marketing data accumulated over the last two decades confirmed that deferiprone-induced agranulocytosis is not dose-related within the therapeutic range, and its occurrence peaks at 5 months after initiation of therapy, declining in frequency after this period. (15) It was concluded that weekly monitoring is a prudent approach but that it does not preclude agranulocytosis from occurring and it could even provide false security, as agranulocytosis could occur shortly after the finding of a normal neutrophil count. The relevance of weekly monitoring of the neutrophil count appears to decrease even further after the first six months of therapy, when agranulocytosis occurs less often. Based upon analysis of data collected over the past 20 years, it appears that patient education may be the key to minimizing risks associated with agranulocytosis during deferiprone therapy. A better approach to minimizing the risks in patients receiving longterm deferiprone therapy is for ANC monitoring to be done weekly only at the beginning of the treatment and to emphasize the importance of educating patients on the need to immediately stop deferiprone and to maintain ANC monitoring upon signs of infection. Based on the conclusions of this review, the frequency of monitoring in this study is reduced: patients who have already been on deferiprone for 12 months in the earlier study, LA38-0411, will now only need to undergo hematology testing monthly, while those who had been on deferoxamine and are now receiving deferiprone for the first time will have their neutrophil count monitored weekly for the first 6 months, biweekly for the next 6 months, and monthly thereafter. Neutropenia management directives (as per Section 7.2.1.8) must be followed at the first sign of neutropenia. Treatment with deferiprone should not be initiated in patients with a history of recurrent neutropenia or an episode of agranulocytosis.

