4 STUDY PROCEDURES

The procedures and assessments to be conducted at each study visit are shown in Table 1.

Table 1 Table of study procedures

Procedure	Visit 1 ¹	Blood Draws ²	Visit 2	Visit 3	Visit 4	Visit 5	Visit 6	Visit 7	Visit 8	Visit 9 or Early Termination
Week:	0		13	26	39	52	65	78	91	104
Informed consent/assent	X									
Eligibility criteria	X									
Prior and concomitant medications	X		X	X	X	X	X	X	X	X
Transfusion information (if applicable) ³	X	X	X	X	X	X	X	X	X	X
Serum pregnancy testing (if applicable) ⁴	X		X	X	X	X	X	X	X	X
Physical examination	X					X				X
Vital signs (including weight and height) ⁵	X		X	X	X	X	X	X	X	X
12-lead ECG	X					X				X
Contraceptive counseling	X		X	X	X	X	X	X	X	X
Serology	X									X
Hematology	X	X	X	X	X	X	X	X	X	X
Biochemistry ⁶	X			X		X		X		X
Serum ferritin	X		X	X	X	X	X	X	X	X
Urinalysis	X					X				X
Liver MRI	X					X				X
Cardiac MRI T2*	X					X				X

Procedure	Visit 1 ¹	Blood Draws ²	Visit 2	Visit 3	Visit 4	Visit 5	Visit 6	Visit 7	Visit 8	Visit 9 or Early Termination
Week:	0		13	26	39	52	65	78	91	104
Dose calculation/verify and adjust dose level	X		X	X	X	X	X	X	X	
Collect used and unused study medication			X	X	X	X	X	X	X	X
Dispense study medication	X		X	X	X	X	X	X	X	
Dispense patient diary card	X		X	X	X	X	X	X	X	
Review and collect diary card			X	X	X	X	X	X	X	
Adverse events	X		X	X	X	X	X	X	X	X

¹ Visit 1 of study LA38-EXT is also the final visit of study LA38-0411. It serves as the baseline visit for those patients who received deferoxamine in LA38-0411 and will now be receiving deferiprone for the first time. (For patients who received deferiprone in LA38-0411, the measures obtained at the baseline visit of the LA38-0411 study will be used as the baseline measures for LA38-EXT as well.)

² For Group 1, hematology testing is to be done monthly throughout the study. For Group 2, it is to be done weekly up to Visit 3 (Week 26), biweekly up to Visit 5 (Week 52), and monthly thereafter. At the quarterly site visits, this testing will be done as part of the routine procedures, and at the other time points it can be done at a local laboratory instead of at the site.

³ Record volume of blood that the patient received during the transfusion, and the mean hematocrit of the packed red blood cell units transfused

⁵ Females of childbearing potential only

⁵ Height will be measured only at Visits 1, 5, and 9

⁶ At Visits 1, 3, 5, 7, and 9, the blood sample must be drawn following a 10-hour fast

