5.2.4 Laboratory Measurements

The following laboratory tests had been performed:

- **Hematology** (for Group 1, monthly throughout the study; for Group 2, weekly for the first 6 months, biweekly for the next 6 months, and monthly thereafter): hemoglobin, total WBC count, ANC, and platelet count
- **Biochemistry** (semi-annually; Visits 1, 3, 5, 7, and 9): total protein, GGT, lactate dehydrogenase (LDH), sodium, potassium, chloride, fasting glucose, total and direct bilirubin (indirect bilirubin will be calculated by the sponsor), AST, ALT, albumin, blood urea nitrogen, calcium, creatinine, uric acid, alkaline phosphatase, and amylase
- **Serology** (Visits 1 and 9): Hepatitis B and C and HIV testing
- **Urinalysis** (annually; Visits 1, 5, and 9): pH, specific gravity, glucose, protein, ketones, blood, and (if indicated by the dipstick results), sediment microscopy. If there is blood in the urine or three or more “plus signs” for protein, samples must be sent for microscopy.
- **Pregnancy** (quarterly; Visits 1–9): serum pregnancy test

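### In Group 2, the timing of short, silent neutropenia is confounded with how often neutrophils are counted, and the SAP has no analysis of confirmed cases that separates the two

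*SAP*

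**What the plan says.** Time to onset of adverse events is a primary endpoint. SAP 6.1.1 defines it as "time to onset (the start date of AE minus the start date of exposure to treatment". For serious events and events of special interest, including neutropenia and agranulocytosis, SAP 6.3.4 states that "the mean time to the first onset and the mean time to the last recurrence will be calculated". The shell that serves Table 14.3.1.10, and the matching one for Table 14.3.1.12, give one N, mean, SD and range per event and group, with a t-test between groups.

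The blood count schedule is in SAP sections 4 and 5.2.4. Group 2, which first receives deferiprone in the extension, is counted "weekly for the first 6 months, biweekly for the next 6 months, and monthly thereafter". For the extension years of the other group: "For Group 1, hematology testing is to be done monthly throughout the study". Its first year on drug took place in LA38-0411, which Protocol 1.2 describes without arm or timing: "Assessments include weekly, biweekly, or monthly monitoring of absolute neutrophil count (ANC". Protocol 1.3 explains that "the frequency of monitoring in this study is reduced" because agranulocytosis is reported to peak at 5 months and then become less frequent.

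Under SAP 5.2.3.1 a case of neutropenia needs two low counts no more than 3 days apart. Under SAP 5.2.3.2 fever or infection calls for a count within 24 hours, whatever the schedule.

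**The concern.** A patient with neutropenia but no symptoms becomes a case only if a count falls inside the episode. In Group 2 the counts thin by roughly 4:2:1 as time on drug grows, so detection falls along the same axis on which onset is measured. A raw mean onset time then mixes when episodes begin with when blood was drawn.

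Long-term safety is the primary objective, and the protocol already expects agranulocytosis to become rarer after the first months. An early mean onset produced partly by the schedule would point the same way as that expectation and could be taken as confirming it. The SAP plans no rate by time on drug, no censoring method and no interval-censored estimate. Patient-years appear only as column totals in the adverse event and concomitant medication shells.

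**Working it through.** The documents give no expected onset time, so there is no planned figure to reproduce. The check asks what the planned mean would show in Group 2 if the true risk were constant.

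**Inputs from the documents.** Follow-up is 104 weeks on deferiprone. The gap G between counts is 7 days to Week 26, 14 days to Week 52, then monthly. Confirmation comes within 3 days.

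**Assumptions.** Onset is uniform over 104 weeks, with no dropout. A month is 28 days and the confirming count comes 2 days after the first. The documents do not give episode length, so it is varied.

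**Step 1: chance of detection.** An episode is found if a scheduled count falls inside it and the count 2 days later is still low.
- Fixed length D: min(1, (D − 2)/G). For D = 7: 5/7 = 0.71, 5/14 = 0.36, 5/28 = 0.18.
- Exponential length with mean m: e^(−2/m) × (m/G) × (1 − e^(−G/m)). For m = 14: 0.68, 0.55, 0.37.

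**Step 2: mean onset of the episodes found.** The three periods last 26, 26 and 52 weeks, with midpoints 13, 39 and 78. The mean is (13p₁ + 39p₂ + 2 × 78p₃)/(p₁ + p₂ + 2p₃). With full detection it is (13 + 39 + 156)/4 = 52 weeks. For D = 7 the weights are 4:2:1, giving (52 + 78 + 156)/8 = 35.8 weeks. Simulation with 2,000,000 episodes per setting dates onset at the detecting count, which adds about one week: 36.8.

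| Assumed length | Weeks 0–26 | Weeks 26–52 | Year 2 | Year 2 / first 26 weeks | Mean detected onset, weeks (simulated) |
|---|---|---|---|---|---|
| 7 days fixed | 0.71 | 0.36 | 0.18 | 0.25 | 36.8 |
| 10 days fixed | 1.00 | 0.57 | 0.29 | 0.29 | 38.3 |
| 14 days fixed | 1.00 | 0.86 | 0.43 | 0.43 | 42.8 |
| 21 days fixed | 1.00 | 1.00 | 0.68 | 0.68 | 48.3 |
| 30 days fixed | 1.00 | 1.00 | 1.00 | 1.00 | 53.4 |
| 7 days exponential mean | 0.48 | 0.32 | 0.18 | 0.39 | 41.8 |
| 14 days exponential mean | 0.68 | 0.55 | 0.37 | 0.55 | 46.1 |
| 28 days exponential mean | 0.82 | 0.73 | 0.59 | 0.71 | 49.3 |

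At 30 fixed days there is no false decline, and detection delay moves the mean slightly later than 52. With a calendar month of 30.4 days the 14-day exponential ratio is 0.52 instead of 0.55.

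**Step 3: symptom-prompted counts.** If a share q of episodes is found whatever the schedule, detection becomes p + q(1 − p). For 10-day episodes and q = 0.5, Year 2 gives 0.29 + 0.5 × 0.71 = 0.64, so the ratio rises from 0.29 to 0.64 and the mean to 47.4 weeks. At q = 1 the ratio is 1.00.

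**Step 4: Group 1.** If its first year was weekly (an assumption) and then monthly, the unbiased mean over 156 weeks is 156/2 = 78. Detected means are 55.4 weeks (10 days), 63.2 (14 days) and 79.5 (30 days).

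**Step 5: the remedy.** With one count every 28 days in all periods of Group 2, the ratio is 1.00 to 1.10 for every length tried and the mean is about 54 weeks. The excess over 1.00 is an edge effect: the grid puts 6 counts in the first 26 weeks and 13 in Year 2, and 13/12 = 1.08.

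Last-recurrence times were not simulated; the same detection argument applies to them.

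**The case against.** **No table can show a decline.** A reader might infer that the planned tables would show neutropenia fading. They cannot: each gives one mean per group, without time bands or trend, and the SAP plans no analysis of decline. This stands. The risk lies in how an early mean is interpreted.

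**The size is assumed.** No episode length is documented, and the effect is absent at 30 fixed days. This stands. Short episodes are at least contemplated: Protocol 7.2.1.8.1 allows 14 days for a detected mild or moderate case to recover before withdrawal. That clock starts at detection, however, and does not tell us how long an unseen episode lasts.

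**Symptoms prompt counts.** This stands, and it applies to every patient. It confines the point mainly to mild or moderate episodes without infection. Extending it to agranulocytosis with the same force is not supported, and Protocol 1.3 reports a real early peak there, so some early clustering is expected.

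**There is a partial safeguard.** SAP Figure 14.3.1.2, extended by its note to ANC, plots the proportion abnormal at each assessment. A proportion per count does not rise merely because counts are frequent. But it shows single-visit abnormality, not confirmed first neutropenia. The hematology shells also run weekly to Week 51 and then quarterly, so the monthly counts between quarterly visits have no rows.

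**Few events.** At 2:1 randomization of 300, Group 2 has at most 100 patients. At the 6.9% for neutropenia in Protocol 1.3 (related events, exposure not stated) that is about 7 events; adding the 7.0% with decreased neutrophil count gives at most about 14. A uniform onset has SD 104/√12 = 30 weeks, so the standard error of the mean is about 11 weeks (n = 7) or 8 (n = 14), against a shift of 6 to 15 weeks (52 − 46 to 52 − 37). This stands as a reason to keep any thinned analysis descriptive, not to make it a condition to pass.

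**Conclusion.** The point holds in limited form. For short neutropenia without symptoms in Group 2, onset timing is confounded with monitoring frequency, and no planned analysis of confirmed cases separates the two. Under a constant true risk and episode lengths of 7 to 14 days (fixed or exponential mean), Year 2 detection is about 0.25 to 0.55 of that in the first 26 weeks, and mean detected onset about 37 to 46 weeks against 52. These figures rest on assumed lengths, 28-day months, a 2-day confirmation gap, no dropout and detection by schedule only.

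Three stronger readings are not supported. One is that any early clustering would come from the schedule alone: the documents fix neither episode length nor the share found through symptoms. Another is that the full weekly-to-monthly sequence applies to everyone: it is documented for Group 2 only, and Group 1's first-year schedule by arm is not given. The third is that long-term safety will necessarily be overstated: that depends on a reader treating the mean as evidence of falling risk, which the SAP does not itself claim.

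**What to change.** In SAP 6.3.4:

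1. Report confirmed first neutropenia per patient-year within each monitoring period (weekly, biweekly, monthly), by group, with exact confidence intervals and the number of counts performed per patient-year alongside. Document Group 1's actual first-year schedule so that its periods can be assigned.
2. Add one descriptive sensitivity analysis from the hematology and local laboratory listings (16.2.9 and 16.2.25), using one count per month plus its confirmatory repeat in every period.
3. State beside Tables 14.3.1.10 and 14.3.1.12 that the mean times to onset and last recurrence are not, on their own, to be read as evidence of a falling risk.

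The cost is some programming: the thinned analysis must derive cases from laboratory values, not adverse event start dates, and for Group 1 it needs the LA38-0411 counts. Intervals will be wide because events are few, and thinning discards counts. No monitoring schedule or clinical rule changes.
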